7.4.6.1.1. Remission Followed by Relapse

The patient achieves remission on all BPRS key symptoms by being rated 3 (which is below clinical threshold) or lower for more than four consecutive weeks at some point following project entry. A rating of ≥ 6 (severe) on any one of these items following this period of remission would meet this relapse criterion.

7.4.6.1.2. Remission Followed by Significant Exacerbation of Symptoms

The patient is rated 3 or lower on the BPRS key symptom items for more than four weeks and the patient subsequently (a) is rated 5 on one of the key symptom items and increases at least two points on another key symptom item within the same four-week period while the initial exacerbating symptom is still in the clinical range (4 or higher) or (b) is rated 5 on one of the key symptom items for more than four weeks.

7.4.6.1.3. Persisting Symptoms Followed by Significant Exacerbation of Symptoms

The patient has persisting clinically significant symptoms in the 4 to 5 range on one or more BPRS key items but not in the 6 or 7 range for more than four weeks (not necessarily always the same item) during the Treatment period without achieving remission (by criteria above), and:

- shows an increase of two points within an eight-week period to a rating of 6 or 7, or
- shows an increase of one point on this item to a 6 and an accompanying two-point increase on another key symptom item within the same four-week period.

These criteria are not made in real time, but are entered into the database and determined at a later time.

7.4.7. Secondary Endpoint Measurements

The secondary endpoints of this study are:

- Role ratings on the Global Functioning Scale (GFS: Role)
- Overall Composite T-score MATRICS Consensus Cognitive Battery (MCCB)

7.4.7.1. Functional Assessment -The Role ratings on the Global Functioning Scale

The GFS: Role ([Cornblatt et al, 2007](#); [Niendam et al, 2006](#)) will serve as the measure of functional outcome for this secondary objective. The GFS: Role is a 10-point rating scale for evaluating school and job functioning. This outcome scale has strong psychometric characteristics and the anchors were developed to be appropriate for adolescents and young adults in a large prodromal schizophrenia study, and are especially suited for the younger age group of our young-adult first-episode sample. GFS: Role will be administered at entry, baseline, and every three months throughout the 12-month Treatment period.

7.4.7.2. Cognitive Assessment- The MATRICS Consensus Cognitive Battery

The Overall Composite T-score from the MCCB is a secondary endpoint and will be the overall index of cognitive performance. This battery is the result of the efforts of a national committee of experts to develop a NIMH-recommended battery for evaluation of interventions designed to improve cognition in schizophrenia ([Kern et al, 2008](#); [Nuechterlein et al, 2008](#)). By using the MCCB, the results of our attempts to improve cognition in schizophrenia can be directly compared to attempts to do so through pharmacological and other learning-based interventions. The Overall Composite Score summarizes performance across 10 tests of Speed of Processing, Attention/Vigilance, Working Memory, Verbal Learning, Visual Learning, Reasoning and Problem Solving, and Social Cognition ([Nuechterlein et al, 2008](#)).

7.4.8. Exploratory Endpoint Measurements

The exploratory endpoints of this study are:

- Heinrichs-Carpenter Quality of Life Scale (QLS)
- Personal and Social Performance Scale (PSP)
- Clinical Global Impressions-Severity (CGI-S)
- Scale for the Assessment of Negative Symptoms (SANS)
- Scale to Assess Unawareness of Mental Disorder-Revised (SUMD-R)
- Glasgow Antipsychotic Side-effect Scale (GASS)
- Modified Medication Satisfaction Questionnaire (Modified MSQ)
- Service Engagement Scale (SES)
- Family Caregiver Medication Administration Hassles scale
- Modified Version of the ACD

7.4.8.1. Heinrichs-Carpenter Quality of Life Scale

The QLS is a clinician-rated scale based on a patient's report during a semi-structured interview. It is used to assess health-related quality of life and functioning in patients with schizophrenia during the preceding four weeks ([Heinrichs et al, 1984](#)). The QLS consists of 21 items in four major domains (Intrapsychic Foundations, Interpersonal Relations, Instrumental Role, and Common Objects and Activities). Following a semi-structured interview, each item is rated on a 7-point scale, from 0 (severe impairment) to 6 (normal or unimpaired functioning). Reported

inter-rater reliabilities range from 0.84 to 0.97 on the summary scales. The QLS will be completed every three months after the onset of randomized treatment. This measure revealed an advantage for aripiprazole monohydrate compared to paliperidone palmitate for improving quality of life in schizophrenia (Naber et al, 2015). The Intrapsychic Foundations subscale will be the primary one analyzed for this objective. This scale will be completed at the time points specified in [Table 2](#).

7.4.8.2. Personal and Social Performance Scale

The Investigator or designee will complete the 5-point PSP scale ([Patrick et al, 2009](#)) at the time points identified in [Table 2](#).

7.4.8.3. Clinical Global Impressions-Severity

The Investigator or designee will complete the CGI-S scale ([Guy 1976](#)) at Screening and at the time points as identified in [Table 2](#).

7.4.8.4. Scale for the Assessment of Negative Symptoms

A SANS manual describes each symptom and provides anchor point definitions. Each of the SANS items are scored on a 6-point Likert-type scale (from 0 to 5). The SANS contains 20 items within five domains of negative symptoms: Alogia; Affective flattening; Avolition-Apathy; Anhedonia-Asociality; and Attention. Each group of symptoms has several component items relevant to the assessment of positive symptoms and a global rating. Negative symptoms will be rated during the administration of the SANS and will be based on observations, information provided by the patient, and from all reliable sources of information. The SANS manual contains a set of specific interview questions, supplemented by our group that will be used by the assessment team to elicit reported negative symptoms (eg, impersistence and asociality). This scale will be completed at the time points specified in [Table 2](#).

7.4.8.5. Scale to Assess Unawareness of Mental Disorder-Revised

The SUMD-R will be used to assess insight in the early course of schizophrenia. To reduce the time burden on patients, the SUMD-R has been shortened to include key items found to be the most useful in previous studies. The SUMD-R measures three aspects of insight for each psychiatric symptom: unawareness that the symptom is present, the attribution as to the cause of the symptom, and unawareness of whether others would perceive the symptom as being present. Unawareness of concentration, memory, and speed of processing deficits are also assessed. The Overall Unawareness of Mental Illness item will be the primary one used for this outcome measure. This scale will be completed at the time points specified in [Table 2](#).

7.4.8.6. Glasgow Antipsychotic Side-effect Scale

The GASS scale will be completed by the patient at the time points specified in [Table 2](#).

7.4.8.7. Modified Medication Satisfaction Questionnaire

The Modified MSQ is a 3-item self-report patient satisfaction questionnaire which assesses the level of patient satisfaction with medication. Patients rate their satisfaction with their current medication, their preference for their current medication versus the one taken prior to the study,

and their opinion on the side effects of their current medication versus the one taken prior to the study. Ratings are on a 5-point Likert scale. The Modified MSQ will be collected every six months following randomization. This scale will be completed at the time points specified in [Table 2](#).

7.4.8.8. Service Engagement Scale (SES)

The SES is a 14-item questionnaire to evaluate engagement with clinical services and to evaluate areas of engagement difficulties that might pose obstacles to treatment. The scale has been shown to have good validity and test-retest reliability ([Tait et al, 2002](#); [Tait et al, 2018](#)). This scale will be completed at the time points specified in [Table 2](#).

7.4.8.9. The Family Caregiver Medication Administration Hassles Scale

The Family Caregiver Medication Administration Hassles scale is a 24-item scale that identifies hassles and frustrations that occur for family caregivers who are responsible for administering medications to their family members. Four subscales have been identified: Information Seeking/Information Sharing, Safety Issues, Scheduling logistics, and Polypharmacy. The overall scale reliability is 0.95, and the test-retest reliability at 2 weeks is 0.84 ([Travis et al, 2003](#)). This scale will be completed at the time points specified in [Table 2](#).

7.4.8.10. Modified Version of the All-Cause Discontinuation

A modified version of the ACD measure used in the CATIE schizophrenia study will be used to track the reasons for medication changes. The modification of this measure pertains to the addition of further nuances in the decision-making process.

7.4.9. Safety Assessments

7.4.9.1. Overview of Safety Assessment Procedures

Each patient will have a treating psychiatrist who is a part of the clinical team for UCLA Aftercare Research Program. The psychiatrist will be responsible for the medical and psychopharmacologic management of patients. The one-on-one medication assessment appointments are scheduled at least monthly, and may be more frequent as per the clinical status and needs of the individual patient. The treating psychiatrists have specialty practice experience in schizophrenia and psychotic disorders, and will be trained in all of the ongoing safety assessments for the study, including:

- Extrapiramidal symptoms (Abnormal Involuntary Movement Scale [AIMS], Barnes Akathisia Rating Scale [BARS], and the Extrapiramidal Symptom Rating Scale [ESRS-A])
- Columbia Suicide Severity Rating Scale (C-SSRS)
- AE collection
- Serious adverse event (SAE) reporting

The treating psychiatrists also attend the UCLA Aftercare Research Program weekly case conferences where the entire clinical team, including the clinical assessors, meets to review the clinical status of all patients in the program. Patients will be reviewed for any SAEs or other

clinical changes on a weekly basis. However, the BPRS assessments that are the basis of the relapse criteria are not specifically reviewed within the case conferences, but salient clinical information gleaned from the biweekly BPRS ratings will be shared at that time and will be used along with all other relevant clinical information for further medication management and patient treatment decisions.

Semi-annual review of all safety assessment responses will be conducted by a Data and Safety Monitoring Committee at UCLA who are not study investigators per the UCLA IRB standards.

7.4.9.2. Extrapyramidal Symptoms

Extrapyramidal Symptom Scales will include AIMS, BARS, and ESRS-A. The Investigator or designee will administer the extrapyramidal symptom scales at time points specified in [Table 2](#).

After administration of the first dose of study drug, if a patient complains of extrapyramidal symptoms (EPS) on days when the abnormal movement scales are not scheduled to be performed, an unscheduled assessment should be performed.

The AIMS will primarily be used to assess dyskinesia. The BARS will primarily be used to assess akathisia. The ESRS-A will primarily be used to assess Parkinsonism and dystonia.

7.4.9.3. Columbia Suicide Severity Rating Scale

The Investigator or designee will administer the C-SSRS according to the schedule in [Table 2](#). At Screening, the “Baseline/Screening” version will be administered ([Mundt et al, 2013](#); [Posner et al, 2009](#); [Posner et al, 2011](#)), and at all other visits, the “Since Last Visit” version will be administered ([Posner K et al, 2009](#)). For “Since Last Visit” versions, patients should be asked to report on ideation and behavior since the last scheduled C-SSRS assessment. The C-SSRS will be administered by a clinician trained to assess and manage suicidal ideation and behavior.

7.4.9.4. Laboratory Assessments

7.4.9.4.1. Drug Testing

A urine drug test for drugs of abuse, including amphetamines, barbiturates, cocaine, methamphetamine, opiates, and phencyclidine will be performed at the time points specified in [Table 2](#). Results must be negative, or if positive, there must be additional evidence that the abuse is not persistent and will not make treatment in this outpatient program contraindicated.

7.4.9.4.2. Hematology, Biochemistry, Metabolic, and Prolactin Assessments

Blood and urine samples for laboratory assessments will be collected at the time points specified in [Table 2](#). Specific hematology, biochemistry, metabolic, and prolactin assessments are listed in [Table 4](#). Samples will be collected in accordance with the site’s usual procedures at the UCLA Department of Pathology phlebotomy station on the first floor of the [name] building next door to the Aftercare Research Program, thereby facilitating convenient blood drawing for laboratory tests.

Table 4: Clinical Laboratory Assessments

Hematology	Biochemistry
Hematocrit	Sodium
Hemoglobin	Potassium
Red blood cell count	Glucose
Total and differential (absolute) white blood cell count	Creatinine
Platelets	Total protein
	Blood urea nitrogen
	Albumin
	Total bilirubin
	Alanine transferase
	Aspartate transferase
	Lactic dehydrogenase
	Gamma-glutamyl transferase
	Alkaline phosphatase
	Creatinine phosphokinase
	A1c
	Blood sugar
	Fasting lipid panel
	Prolactin

7.4.9.4.3. Plasma Aripiprazole Concentrations

Plasma samples will be collected at the visits indicated in [Table 2](#) and will be kept for measurement of aripiprazole concentrations in plasma assays. The clinicians will not be updated on the outcome of the measurement.

7.4.9.4.4. Pregnancy Testing

A serum pregnancy test will be conducted at Screening and at the last study visit for all women. A urine pregnancy test will be administered to all women every 3 months during the Treatment period, as specified in [Table 2](#). At the Screening visit, results must be negative for the patient to be eligible for the study.

7.4.10. Vital Signs

Vital signs (i.e., blood pressure, pulse, respiratory rate, and oral body temperature) will be assessed at the time points specified in [Table 2](#). Blood pressure, pulse, and respiratory rate will be measured after the patient has been resting in a seated or supine position for at least five minutes.

7.4.11. Physical Examination, Body Height, Weight

A physical examination will be performed at the time points specified in [Table 2](#).

7.4.12. Adverse Event Monitoring

Continuous monitoring of AEs will take place from the time a patient signs the informed consent document until the completion of the final study visit. Additional information on the assessment of safety is provided in Section 11.

7.4.13. Randomization

Randomization will occur after the Stabilization period in a 1:1 ratio by an automated method at UCLA. Patients successfully completing the Stabilization period will be randomized to one of two medications groups: converting from oral antipsychotic to AL-LAI vs continuing on (ARI ORAL). Each medication group will be further randomized to the cognitive remediation or healthy behavior training condition. Patients do not need to be free of psychosis at the time of randomization and the severity of psychosis is not a variable for stratification.

7.5. Study Requirements and Restrictions

Prohibited medications are defined in Section 7.5.1. Other restrictions are outlined in the Exclusion Criteria (Section 6.2). If at any point a patient is no longer eligible per the entry criteria, they will be discontinued from the study.

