Randomization to ARI-ORAL: Patients will continue with ARI-ORAL doses within the recommended oral dosage range for the treatment of schizophrenia (10-30mg/day) with the usual starting dosage of 10 mg/day. ARI-ORAL dosage will be flexible and dosage will be at the discretion of the treating psychiatrist. Patients assigned to this treatment arm will receive a written prescription for a 30-day supply along with a medication coupon so there will be no medication cost to the patient.

Discontinuation of Assigned Treatment

Both groups will remain on their assigned treatment for 12 months or discontinue their assigned medication early. The reason(s) for early discontinuation of initial antipsychotic will be recorded, including whether it is initiated by the clinician or patient, and whether it is efficacy or tolerability related. Patients will be assessed for the reason for discontinuation using a version of the All-Cause Discontinuation (ACD) measure that was the primary outcome of the CATIE schizophrenia study. If a switch to another antipsychotic medication is warranted, the new therapy will be determined by the prescribing psychiatrist's judgment using the medication selection recommendation adapted from NAVIGATE pharmacologic treatment manual developed as part of the Recovery After an Initial Schizophrenia Episode (RAISE) study intervention groups. Patients discontinuing study drug after Randomization, but remaining in active treatment and follow-up, may be prescribed any first-line oral antipsychotic within the prescribing information dosage for schizophrenia. Patients will be encouraged to stay in the study for the remainder of the 12-month Treatment period and will be administered all of the scheduled assessments even if the initial randomly assigned antipsychotic medication is discontinued by the treating psychiatrist.

Symptom assessments will occur every two weeks, functional endpoint will occur every three months, and the cognitive endpoint will occur at baseline and at the 6- and 12-month points. All patients participating in the protocol will be invited to concurrently participate in a separate NIMH-funded psychosocial intervention protocol comparing the effectiveness of computerized cognitive training with and without aerobic exercise training.

Number of Patients Planned: Approximately 128 patients enrolled into the Stabilization period for final randomized sample of 90 (45 in each group) with a target of 14 relapses

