6.2. Exclusion Criteria

Each patient must not have any of the following conditions to be qualified to participate in this study.

1. Evidence of a known neurological disorder (e.g., epilepsy) or significant head injury with loss of consciousness of more than one hour.
2. Has mental retardation (i.e., premorbid IQ less than 70) as estimated by the Wechsler Test of Adult Reading (WTAR) completed at screening or as documented in medical records conducted in childhood. The WTAR assesses word pronunciation, which is thought to be unaffected by cognitive decline associated with neurological damage and is thus a good proxy for premorbid intelligence.
3. Is currently pregnant or breastfeeding, or is planning to become pregnant during the study.

4. Is currently on a long-acting injectable antipsychotic medication and it is clinically contra-indicated due to the risk of becoming a danger to self or others if the patient discontinued treatment with the long-acting injectable in order to participate in this trial.
5. Has a history of poor or inadequate response to an adequate trial of oral or injectable aripiprazole (does not exclude patients whose aripiprazole exposure was too brief or at sub-therapeutic doses).
6. Has received AL-LAI or IM depot aripiprazole within two months prior to Randomization (unless Stabilization period is extended beyond 90 days to accommodate).
7. Has alcohol or substance abuse as a prominent clinical problem or makes the primary diagnosis not possible to confirm. Evidence of alcohol or substance use is not, in and of itself, exclusionary.
8. Is currently being treated with clozapine.
9. Has participated in a clinical trial involving any drug within the past two months prior to screening, or is currently participating in a clinical trial involving an investigational medication.
10. Has a history of psychopathology based on the screening SCID other than schizophreriform disorder, schizophrenia, or schizoaffective disorder, mainly depressed type as indicated by any primary DSM-5 diagnosis within the 12 months prior to Screening or Randomization (e.g. primary diagnosis of bipolar disorder, schizoaffective disorder, bipolar type, bipolar disorder, or neurocognitive disorder) based on our research diagnostic procedures.

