6.3. Discontinuation of Assigned Medication

If the randomly assigned medication must be discontinued and/or switched to a different antipsychotic medication, the patient may remain in the study until the 12-month assessment point. End of Assigned Treatment assessment point measures will be completed as close to and if possible, just prior to, the discontinuation/switch. Decision to switch medication will be recorded on a modified Clinical Antipsychotic Trials of Intervention Effectiveness (CATIE) All-Cause Discontinuation (ACD) assessment completed by the treating psychiatrist (Stroup et al, 2003). The switch to another antipsychotic medication will be guided by clinician judgment using the medication selection recommendation adapted from the oral antipsychotic guidance used in the RAISE study (Kane et al, 2015). The date the new medication is prescribed will be recorded and used in the analyses. Patients who choose to discontinue study medication will be allowed to re-

initiate study medication at any time during the 12-month follow-up. All other regular assessments will be completed throughout the remainder of the 12-month study.

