Efficacy will be evaluated based on the Brief Psychiatric Rating Scale (BPRS) scored for symptom exacerbation or relapse following Subotnik et al. ([Subotnik et al, 2015](#)) and Nuechterlein et al. ([Nuechterlein et al, 2006](#)). Because patients will not be withdrawn from the study if relapse criteria are met, there will be no need to score the BPRS for relapse contemporaneously throughout the study. Secondary outcomes will be role functioning and cognition. Exploratory outcomes will be negative symptoms, suicidality, awareness of having a mental disorder, extrapyramidal and prolactin-related side effects, service engagement, treatment satisfaction, and quality of life. Safety assessments will be collected and monitored.

Figure 1: Study Design

^a 1 to 3 months of stabilization on oral aripiprazole.

^b For 2 weeks prior to Randomization, all patients must be on oral aripiprazole

^c Initiation of treatment per Section 7.2.2

Abbreviations: ARI-ORAL: aripiprazole oral; AL-LAI = aripiprazole lauroxil long-acting injectable; ET = End Treatment; EoS = End of Study

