8.1. Study Drug Dose and Administration

During the 12-month Treatment period, patients who tolerate the study medication but find that after adequate duration and dosage, it is inadequately efficacious per clinical judgment, may be switched to another oral antipsychotic at the discretion of the Investigator. Patients who miss scheduled injections or visits are allowed to continue in the same assigned treatment group.

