10.1.2. Primary Endpoint Rationale

The expanded BPRS (Ventura et al, 1993) will be rated every two weeks, with each item rated from 1 (not present) to 7 (extremely severe). Positive symptom exacerbation or relapse will be identified based on increases of the BPRS items Unusual Thought Content, Hallucinations, or Conceptual Disorganization using computer scoring algorithms (Nuechterlein et al, 2006). The three scoring categories considered to be a psychotic symptom return are: “Remission Followed by Relapse”, “Remission Followed by Significant Exacerbation”, or “Persisting Symptoms Followed by Significant Exacerbation.” These definitions do not consider other aspects of outcome often part of “treatment failure” definitions, such as: hospitalization or increased treatment to prevent hospitalization; harm to self, others, or property; arrest; or treatment discontinuation, as these other negative outcomes might not be secondary to psychotic symptoms per se. These classifications have been shown to be sensitive measures of the return of psychotic symptoms and differentiated oral and long-lasting injectable treatment groups in our previous research (Subotnik et al, 2015). Patients in the proposed study will continue in the protocol even if a psychotic relapse or exacerbation occurs, although the medication regimen might change at the discretion of the Aftercare Research Program treating psychiatrist. Our experience has been that the majority of psychotic exacerbations or relapses can be managed on an outpatient basis unless the patient has concurrent imminent suicidality, and often the prescribed medication does not change (although the dosage might). Continuing patients in the protocol after a return of symptoms will allow us to assess secondary outcomes at the 6- and 12-month points.

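### Section 7.5 discontinues patients who lose eligibility without limiting this to the period before Randomization; read literally, it conflicts with the planned assessment of randomized patients to Month 12.

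*Combined protocol and SAP*

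**What the plan says.** Section 7.5 (Study Requirements and Restrictions) gives the withdrawal rule: "If at any point a patient is no longer eligible per the entry criteria, they will be discontinued from the study". The sentence before it points to the exclusion criteria in Section 6.2 as further restrictions.

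Other sections describe follow-up after Randomization:

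- **Synopsis, Discontinuation of Assigned Treatment:** patients are encouraged to stay for the rest of the Treatment period and "will be administered all of the scheduled assessments even if the initial randomly assigned antipsychotic medication is discontinued by the treating psychiatrist".
- **Section 6.3:** "If the randomly assigned medication must be discontinued and/or switched to a different antipsychotic medication, the patient may remain in the study", up to the Month 12 assessment. The section adds that the other regular assessments are completed over the remainder of the study.
- **Section 7.1:** relapse need not be scored as the study proceeds, for this reason: "Because patients will not be withdrawn from the study if relapse criteria are met".
- **Section 10.1.2:** "Patients in the proposed study will continue in the protocol even if a psychotic relapse or exacerbation occurs".

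Two further places assume that switched patients stay. Table 2, footnote 3, allows end of study treatment to fall on a therapy other than aripiprazole. Section 8.2 tracks adherence to other oral antipsychotics after a switch from ARI-ORAL.

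**The concern.** The rules have different triggers (lost eligibility in one, and drug discontinuation, switch or relapse in the others), but they can meet in the same patient. No section says which prevails.

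The retention rules protect the analysis: patients who do badly on assigned treatment still contribute outcome data. Anyone applying Section 7.5 as written could undo this for some of those patients. Removal would follow from clinical course, and in an open-label study the judgement is made knowing the arm. A patient removed before a qualifying BPRS rating is lost to the primary endpoint from that date, and the later GFS: Role and MCCB assessments are lost too.

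**Working it through.** The question is one of text, and no figure in the plan is contested, so the check sets the sections side by side.

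**1. Scope of the Section 7.5 sentence.** It is mandatory, it is not limited to the time before Randomization, and its consequence is leaving the study. The surrounding section also governs conduct after Randomization: Table 5 has a column for medications started after it, and Section 7.5.2 covers contraception during and after the study. The sentence's position therefore does not confine it to screening.

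**2. Clearest overlap: switch for inadequate efficacy.** Section 8.1 covers patients who tolerate study drug but for whom, in its words, "after adequate duration and dosage, it is inadequately efficacious per clinical judgment, may be switched to another oral antipsychotic". Exclusion 5 in Section 6.2 reads "Has a history of poor or inadequate response to an adequate trial of oral or injectable aripiprazole", sets aside exposures that were too brief or too low, and states no time point. Both arms receive aripiprazole, one oral and one injectable. Both texts can therefore be read as describing the same patient. The Synopsis and Section 6.3 then keep the patient under assessment, while Section 7.5, read literally, removes the patient.

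**3. Weaker overlap: imminent danger to self.** Exclusion 11 opens without a time point, but its next sentences concern the two weeks before entry and an extension of Stabilization. Section 10.1.2 says that most relapses can be managed as outpatients "unless the patient has concurrent imminent suicidality". That phrase concerns the setting of care, not exit from the study, and the same paragraph continues relapsed patients in the protocol. An overlap is possible on a literal reading, but it is less direct than in step 2.

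**4. Evidence of intent.** Section 7.4.3 ties eligibility review to the visits in Table 2, which marks Screening and Day 1 only. Footnotes 1 and 3 of Table 5 speak of ending, or not ending, the treatment assignment rather than the study. With the switch provisions, this points to a pre-randomization intent. No sentence states that intent.

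**5. Consequence for the analyses.**

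- *Analysis set.* The ITT definition in Section 12.2.1 keeps a removed patient in the analysis but cannot restore lost follow-up.
- *Primary endpoint.* Section 12.4 gives no censoring rule for the Cox model. Some qualifying events take time to establish: Section 7.4.6.1.2 includes a rating of 5 for more than four weeks, and Section 7.4.6.1.3 uses four- and eight-week windows. A patient removed while worsening could leave before qualifying. A relapse whose ratings are already recorded still counts, because scoring is done later from the database.
- *Secondary endpoints.* Section 12.4 relies on data being missing at random. Removal for reasons tied to clinical course makes that harder to defend.

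**6. Size.** The documents give no rate of eligibility lost after Randomization and no split by arm. Some such removals may already lie within the 20% attrition assumed in Section 12.1.1. Neither a count nor a direction of bias can be calculated.

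**The case against.** The strongest reply is that specific provisions outweigh a general sentence. The protocol plans repeatedly and in detail for patients who switch, so Section 7.5 is unlikely to have been meant to override those plans. Exclusion 5 speaks of a history of poor response, under a lead-in about qualifying to participate; treating on-study failure of the randomized drug as lost eligibility is strained. This stands as evidence of intent. It does not supply the missing limit: the sentence still applies at any point, and staff following it literally would have textual support.

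Three stronger readings are tempting but not supported:

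- A reader might infer that relapsed or switched patients must be withdrawn. Sections 7.1 and 10.1.2 say the opposite for relapse, and the Synopsis and Section 6.3 do so for switches. The conflict arises only where an entry criterion is also read as newly met.
- A reader might treat every criterion without a date as a trigger after Randomization. Absence of a date does not show that. Exclusion 4, for example, concerns stopping a prior injectable in order to join and is in substance a pre-entry matter. For substance abuse that emerges during treatment, no section specifically promises follow-up, and Section 7.4.9.4.1 leaves room for judgement on positive drug screens.
- A reader might infer a definite loss of power or a bias towards one arm. Neither follows: the frequency is unknown, and removed patients contribute follow-up time until removal.

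Pregnancy does not settle the matter either. Section 7.5.2 stops study drug, whereas Section 11.1 withdraws the patient from the study. That is a separate inconsistency.

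**Conclusion.** The concern holds as a conflict of wording that can affect outcome data. Section 7.5, read literally, ends follow-up for some randomized patients whom the Synopsis and Sections 6.3, 7.1 and 10.1.2 plan to assess to Month 12. The overlap is clearest for a switch for inadequate efficacy. The sponsor probably meant the rule to apply before Randomization, but the text does not say so.

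The consequence is conditional: if the sentence is applied literally, there is a risk of informative censoring in the primary analysis and a weaker missing-at-random assumption in the secondary ones. Its size and direction cannot be derived from the documents. Over-enrollment under Section 6.4 could make up the number of relapses but would not remove a bias. The point should be fixed because the change is small. Confidence is medium, because the conflict depends on the literal reading.

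**What to change.** Reconcile Section 7.5 with the Synopsis and Sections 6.3, 7.1 and 10.1.2:

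1. Limit study discontinuation for lost eligibility to the period before Randomization.
2. State that after Randomization the BPRS, GFS: Role and MCCB assessments already scheduled continue to Month 12 unless consent is withdrawn, the patient cannot be followed, or another section expressly requires withdrawal from the study.

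Decisions on study drug and clinical management stay where the protocol puts them. The sponsor should separately reconcile Sections 7.5.2 and 11.1 on pregnancy; the change proposed here does not decide that question.

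The cost is a short amendment and continued assessment of what is likely to be a few patients, at visits already in Table 2.
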